Diagnostic test/procedure (research-related diagnostic test or procedure)

Obtaining human tissue for basic research or biospecimen bank

Survey instrument

None of the above

The following documents are currently attached to this item:

There are no documents attached for this item.

Department budget code

None

Protocol**Objectives****Overall objectives**

We aim to develop a Gym where sensitized, wireless toys are strategically hung and placed within reach of infants to elicit toy-oriented body and arm/hand movements. Each toy will be equipped with sensors capable of measuring the infant's grasping actions such as squeezing, pinching, tilting, etc. A low-cost 3D motion capture system will be used to collect video data and the infants' reaching and body kinematics in response to the toys. A pressure mat will be used to measure postural changes to detect weight shifts, rolling, crawling and other movements away from the initial posture. By capitalizing on these wireless and low-cost technologies, it will permit the regular and non-invasive monitoring of infants, which can lead to detailed, non-obtrusive, quantitative evaluation of motor development. In this vein, we also aim to conduct proof-of-concept testing of the Gym with atypical and typical developing infants. We will include infants' ages 3 to 11 months who are categorized as high-risk or low-risk using the Bayley Infant Neurodevelopmental Screener.

Background

An estimated 5 to 10 percent of children have developmental disabilities (Rydz 2005), and an increase in survival rates of medically fragile infants has led to an increased number of children with functional impairments later in life (Vohr et al 2003). Particularly, pre-term and low birth weight infants as well as those exposed to brain injuries due to a central nervous injury insults such as asphyxia, neonatal seizures, prenatal drug use, or maternal infections are at increased risk for developmental delays and neurologic impairment. Successful early detection of delay or impairment in at-risk infants depends on the effectiveness of standard clinical scales, many of which are not sufficiently sensitive to screen infants younger than 6 months (Leonard et al 2001). For example, one popular scale was reported to have a positive predictive value of 67 percent for motor or cognitive impairment, i.e., high risk infants identified at 6 months using the screening tool were 67 percent likely to have a cognitive impairment at

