The proposed research is specifically designed to investigate the ability of a novel tool to identify atypically developing infants from their typically developing peers. There will be an initial portion for usability feedback of hardware and software. For testing: For the first portion of the study (Part A) we will recruit up to 10 infants for analysis for up to two sessions each. After this initial testing, twenty-four infants will be recruited to participate, including 12 who are developing typically and 12 who are identified as at-risk for neuromotor delay. Infants with typical development will be at least 3 months and less than 11 months of age, score in the low-risk category on the Bayley Infant Neurodevelopmental Screener (BINS), score a greater than 85 on all sub-scales of the Bayley Scale of Infant Development (BSID-II), have no history of significant cardiac, orthopedic, or neurological condition, and gestational age at least 37 weeks. Infants at risk for neuromotor delay will be at least 3 months and less than 11 months of age (corrected for preterm birth if applicable), score in the moderate or high risk categories on the BINS, and score an 85 or less on the motor sub-scales of the Bayley Scale of Infant Development (BSID-II). In an effort to decrease variability of the data, infants in each group will be further stratified into an older group (8-10+ months) and a younger group (3-5 months).

Study duration

1) We estimate that it will take two years from the date of IRB approval to enroll all subjects and complete the study. 2) At minimum, some subjects may be asked to experienced the Gym 1x. At most, a subject will be asked to use the Gym for up to 5 consecutive days. Each day the infant will use the gym, both with and without toys, for 3 minutes. 3) 5/01/2015 - 8/01/2017

Characteristics of the Study Population

Target population

Two populations will be involved: 1. Infants exhibiting typical development between 3 months and 11 months of age 2 . Infants exhibiting atypical development (at-risk for neuromotor delay) between 3 months and 11 months of age.

Subjects enrolled by Penn Researchers

50

Subjects enrolled by Collaborating Researchers

0

Vulnerable Populations **Children Form**

Pregnant women (if the study procedures may affect the condition of the pregnant woman or fetus) Form

Fetuses and/or Neonates Form

Prisoners Form

Other

None of the above populations are included in the research study

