
The following documents are currently attached to this item:

There are no documents attached for this item.

Deception

Does your project use deception?

No

International Research

Are you conducting research outside of the United States?

No

Analysis Plan

We will identify a battery of metrics derived from kinematic and kinetic measurements of infant movement that are able to discriminate between atypical and typical infants and evaluate neuromotor impairments. Metrics quantifying one and two-handed reach and grasp actions as well as leg and body actions will be derived from the data. We will also determine the reliability/reproducibility of our methods across the repeated measurements taken in the home. We also will examine how each metric correlates with the BINS and BSITDIII scores. The key primary metrics are unimanual and bimanual arm use, leg use, grasp forces, arm position when being used, and arm velocity when used. Secondary measures will be center of pressure from starting position, toy speed, toy acceleration, toy tilt angle, arm synchronicity, leg synchronicity, leg distance to toy, and respective differences in the percentage of arm use for reaching and for grasping. Given our long-term goal of detecting the emergence or lack of emergence of multiple milestones in the development of infants, we will examine a variety of metrics. Some of these milestones are the emergence of hand dominance using the relationship between the right and left hands; the emergence of unimanual or bimanual reaching using the relationship of the hand position to the toy, the hand speed, the frequency of movements; the emergence of unimanual grasping using grasping forces, the emergence of undifferentiated bimanual grasping detected by monitoring when the right and left arms start to move together toward a toy, and the emergence of differentiated bimanual grasping. For each variable, we anticipate having 120 data points per second for a minimum of 180 seconds. Initially, kinetic metrics, and frequency of reaching and grasping will be summarized using means and standard deviations each day, to assess for variability. Intraclass correlations coefficients (ICC) will be calculated to examine reliability/reproducibility of each measurement over the 5 days. If the ICCs are relatively high (.9), we will average the 5 days to create a single summary figure for each measurement to test. Using these summary figures, we will first perform 2-sample t-tests or Wilcoxon rank sum tests on the averages or ranks of each metric respectively, where the two groups represent atypical and typical infants, stratified by age group. Given our stratified groups of younger/older and typical/atypical infants, we anticipate having relatively large differences across most measures. Should the ICCs be low, due to learning we will use a 2-factor ANOVA in repeated measures where day would be the repeated measure and age group and infant type would be the 2 factors. For non-normal distributions, such as many zeroes for the atypical group or other non-normal/skewed distribution, we will use either Poisson (log-linear) regression or a Negative Binomial (ZINB) regression. All analyses will be performed using SAS statistical software. As we are looking for proof of concept, we will be looking for relatively large differences between atypical and typical babies. In order to build a machine algorithm to analyze the baby data, we will build a test data set from publically held YouTube videos. We will pull YouTube videos from babies between the ages of 1 month and 12 months.

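### The study asks whether the Gym can tell atypical from typical infants, but no estimate of discrimination with an interval (such as an AUC) is planned, and the correlations with the group-defining scores are not specified as pooled or adjusted.

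*Combined protocol and SAP*

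**What the plan says.** The Design section says the study is meant to "investigate the ability of a novel tool to identify atypically developing infants from their typically developing peers". The Overall objectives describe the intention to "conduct proof-of-concept testing of the Gym with atypical and typical developing infants". The Analysis Plan sets out to find "a battery of metrics derived from kinematic and kinetic measurements of infant movement that are able to discriminate between atypical and typical infants" and lists the main candidates: "The key primary metrics are unimanual and bimanual arm use, leg use, grasp forces, arm position when being used, and arm velocity when used".

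The planned outputs, all in the Analysis Plan, are:

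- daily means and SDs, and ICCs over the five days;
- if ICCs are high (.9), five-day averages, on which "we will first perform 2-sample t-tests or Wilcoxon rank sum tests on the averages or ranks of each metric respectively", stratified by age group;
- otherwise, "Should the ICCs be low, due to learning we will use a 2-factor ANOVA in repeated measures";
- for skewed or zero-heavy data, "we will use either Poisson (log-linear) regression or a Negative Binomial (ZINB) regression";
- correlations of each metric with BINS and Bayley scores.

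On size, the plan says only: "As we are looking for proof of concept, we will be looking for relatively large differences between atypical and typical babies". It gives no alpha, no numerical difference, and no AUC, sensitivity, specificity or confidence interval.

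The Design section forms the groups of 12 and 12 from the same instruments used in the correlations. Typical infants are BINS low-risk and above 85 on every Bayley sub-scale. At-risk infants are BINS moderate or high risk and at 85 or below on the Bayley motor sub-scales. The edition is BSID-II there and BSITDIII in the Analysis Plan.

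**The concern.** The question is how well a metric separates two kinds of infant. The planned analyses ask whether the group averages differ. A clear difference in means can coexist with considerable overlap, so a reader would learn that a metric differs between groups without learning how accurate it is or how uncertain that accuracy is. The Background motivates the study with an accuracy figure for an existing scale (a positive predictive value of 67 percent), yet the plan yields no accuracy figure of its own.

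The correlations raise a smaller issue. The groups are cut on BINS and Bayley scores, so a correlation pooled over all 24 infants partly restates the group contrast. The plan does not say whether the correlations are pooled or adjusted.

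**Working it through.** The plan gives no power, alpha or effect size, so there is no figure to reproduce.

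**Inputs.** From the Design section: 12 typical and 12 at-risk infants in two age bands. Assumed: two-sided alpha 0.05, 6 v 6 in each band, and, for the t-test conversions, normal metrics with equal SD.

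**1. Accuracy implied by a just-significant result.**

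For the t-test, the smallest significant observed difference is d = t(0.975, 2n-2) x sqrt(2/n). Then AUC = Phi(d/sqrt 2), and sensitivity at 90% specificity = Phi(d - 1.2816).

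- n = 12 per group: d = 2.074 x sqrt(2/12) = 0.847; AUC 0.73; sensitivity 33%.
- n = 6 per group: d = 2.228 x sqrt(2/6) = 1.286; AUC 0.82; sensitivity 50%.

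For the exact Wilcoxon test, the observed AUC is 1 - U/(mn), with U the smaller statistic.

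- 12 v 12, ages combined: U <= 37 of 144 (p = 0.045); AUC 1 - 37/144 = 0.743.
- Two 6 v 6 strata summed: U <= 18 of 72 (p = 0.046); AUC 1 - 18/72 = 0.75.
- One 6 v 6 band alone: U <= 5 of 36 (p = 0.041); AUC 1 - 5/36 = 0.861.

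Stratifying the tests by age group can mean a combined stratified test or a separate test in each band, and the plan does not say which. Both sets of figures therefore apply.

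**2. Precision of an added AUC.**

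The Hanley-McNeil variance for n v n is V(A) = [A(1-A) + (n-1)(Q1 - A^2) + (n-1)(Q2 - A^2)]/n^2, with Q1 = A/(2-A) and Q2 = 2A^2/(1+A). The average of two 6 v 6 strata has half the 6 v 6 variance.

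- At an observed AUC of 0.80, the score-type limits solve (0.80 - A)^2 = 1.96^2 x V(A)/2, giving 0.56 to 0.92.
- The Wald interval at 0.80 is 0.80 +/- 1.96 x 0.095 = 0.61 to 0.99.
- At 0.90 the Wald upper limit is 0.90 + 1.96 x 0.069 = 1.035, beyond the possible range. This is why a plain Wald interval should be avoided.

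**3. Pooled against adjusted correlation.**

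This was simulated with 24 infants per study and 10,000 studies. The Bayley score is taken as mean 100, SD 15, cut at 85. The adjusted correlation allows for group and corrected age (20 df).

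| Truth | Pooled r (significant) | Adjusted r (significant) |
|---|---|---|
| 1.2 SD group gap, no relation within groups | 0.43 (60%) | 0.00 (5%) |
| Linear correlation 0.4 throughout | 0.44 (61%) | 0.27 (23%) |

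The near match of the pooled values depends on the assumed at-risk score distribution. With an underlying at-risk mean of 80 instead of 100, pooled r is 0.44 v 0.50 and adjusted r is 0.00 v 0.30. In either case the pooled value alone separates the two situations poorly.

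**The case against.** **This is a 24-infant proof of concept looking for sizeable differences.** That is a fair description, and the intention is oriented to effect size. But the size is never quantified, and a descriptive estimate adds no hypothesis and no infants.

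**Significance here may already mean good discrimination.** This holds if each age band is tested separately, where the just-significant AUC is 0.82 to 0.86. A reader might infer that the plan would pass metrics of modest accuracy. That follows only on the combined 12 v 12 reading, and the plan does not settle which applies.

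**The plan does not say that significance makes a metric discriminating.** Correct. A reader might infer such a rule from the sequence of tests, but the documents state neither the rule nor an alpha. The supportable point is that no accuracy estimate is planned.

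**An AUC can be derived from the planned results.** In part: the Wilcoxon statistic divided by the product of the group sizes is an AUC, and means and SDs give one under normality. It is still not a planned output and has no interval, and the count models do not give one directly.

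**The machine algorithm may supply accuracy.** The Analysis Plan mentions an algorithm and a YouTube data set, but no performance measure and no BINS or Bayley reference for the videos. It would be too strong to say that the study has no classifier; none is described.

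**The correlations are exploratory and the adjusted version has little power.** Both are true, which is why this part is secondary and both versions are requested.

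**Conclusion.** The concern holds as a gap between the stated aim and the planned outputs. The planned tests are not invalid. The plan asks about identification and discrimination but provides no discrimination estimate or interval. A bare significant result is compatible with an AUC as low as about 0.73 to 0.75 on the combined reading, or 0.82 to 0.86 on the separate-band reading, so it does not convey accuracy or its uncertainty. These figures assume alpha 0.05 and an even age split; the t-test figures also assume normality and equal SDs.

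The correlation point is secondary. It would be wrong to conclude that a pooled correlation is spurious: it mixes the group contrast with any relation inside the groups, and the adjusted value is weakened by the restricted score range. Neither is sufficient alone.

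The change is worth making and cheap. It does not affect design, sample size or conduct.

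**What to change.** Keep the planned tests and add to the Analysis Plan:

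1. For each key primary metric, a descriptive age-stratified AUC (atypical v typical) with a 95% interval of score or logit type, not plain Wald.
2. The data it uses: the same per-infant summary as the test, after the no-toy adjustment described under Procedures. When ICCs are high, this is the five-day mean. When they are low, give the five-day-mean AUC as a descriptive supplement to the repeated-measures ANOVA, or give the AUC by day.
3. BINS and Bayley correlations both pooled and adjusted for group and corrected age. Note that the pooled value partly restates the group contrast, and that the adjusted value is attenuated and has low power, so a null adjusted result is not evidence of no relation.
4. One Bayley edition, reconciling BSID-II in the Design section with BSITDIII in the Analysis Plan.

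If a multi-metric battery is later put forward, its selection and validation would need describing; nothing is needed now.

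**Cost.** Some wording and a little programming on data already to be collected. Intervals will be wide, about 0.56 to 0.92 at an AUC of 0.80. The AUC may also overstate screening accuracy. Infants with discordant BINS and Bayley results are excluded, and typical infants must be term-born without significant cardiac, orthopedic or neurological history. The report should say that it describes two separated groups.

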The following documents are currently attached to this item:

There are no documents attached for this item.

Subject recruitment

Infants with typical development will be recruited from siblings of patients at The Childrens Hospital of Philadelphia (CHOP), and through local parent groups. Potential candidates in the at-risk group will be invited to participate through a variety of mechanisms within CHOP. The primary avenue for recruitment will be through the Neonatal Follow-up clinic at CHOP. Infants who are receiving services at the Center for Rehabilitation will also be invited to participate. In efforts to recruit a population that is easily testable on multiple days, testing may be done at a local daycare.

Will the recruitment plan propose to use any Penn media services (communications, marketing, etc.) for outreach via social media avenues (examples include: Facebook, Twitter, blogging, texting, etc.) or does the study team plan to directly use social media to recruit for the research?

No

The following documents are currently attached to this item:

There are no documents attached for this item.

Subject compensation*

Will subjects be financially compensated for their participation?

Yes

The following documents are currently attached to this item:

There are no documents attached for this item.

If there is subject compensation, provide the schedule for compensation per study visit or session and total amount for entire participation, either as text or separate document

For the usability portion the individual caregivers will be compensated 10 dollars. Part A Families will be compensated 50 dollars for the testing. Families participating in Part B will be compensated 100 dollars for their first visit (clinical evaluation plus first gym session) and 25 dollars for each session thereafter (\$200 total). Should the authorized representative of the research participant (infant) decide to withdrawal prior to completion of the study, compensation will be prorated. Compensation will be through a reloadable ClinCard. Any daycare that agrees to participate in the study will also receive a 100 dollar gift card for infant/children's toys and activities.

Study Procedures

Suicidal Ideation and Behavior

Does this research qualify as a clinical investigation that will utilize a test article (ie- drug or biological) which may carry a potential for central nervous system (CNS) effect(s)?

No

Procedures

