Prior to being assessed by the therapist, the parent or legal guardian will be consented. They will also be asked to fill out general surveys including, a demographic survey, and a case report form, and a user feedback survey which provides relevant information, on both the family's and infant's medical history and experience. After being assessed by a certified therapist for approximately one hour, both atypical and typical infants will be observed playing within the Gym. The environment will be prepared such that only items safe for infants will be in the testing and play areas. For the usability: The caregiver may be asked to closely observe and examine the hardware and the software of the system. The caregiver may then offer the toy to the infant for familiarization, observe the infant play and capture and upload a video of this interaction. The caregiver may be asked to complete a feedback and observation survey that will provide relevant information about the interaction and software and hardware experience. Part A) Data quantifying infants actions with and without toys will be collected in one or two sessions. Infants will be tested for their reaction to the gym without toys and then their reactions with 1 or multiple toys. The baby will be placed in the center of the gym. The baby will be allowed to settle and play for 1 minute then data will be collected again for 1-3 minutes. Each session will be recorded using the Microsoft Kinect camera. Arm/hand/leg position data will be collected with the Kinect camera, grasp pressure and forces will be collected, toy position and angular data will be collected via Kinect and inertial sensors, and central pressure data will be collected via the novel mat. Video data mapping their reaction may be collected using "Autism and Beyond" developed for research by Duke University. Part B) Data quantifying infant actions will be collected for 5 consecutive days under two conditions: with toys and without toys (control); the no toys condition will be tested first and the toy condition immediately after. The data from the no toy condition will be used to adjust the observations in the toy condition and will be used to account for the infants baseline actions per day. A test session will proceed as follows: First, the infant will be placed on his or her back at a pre-determined position on the gym mat in the no toy condition. Data will be collected for 3 minutes. The infant will be removed. The toys will be placed in the gym and adjusted for the infant reach; hanging toys will be placed at about 75% of the infants reach. After, the infant will be placed again with respect to the pre-determined position. To detect an infants intentional movement toward a specific toy, the location of each toy will be randomized within possible locations per toy type. The baby will be allowed to settle and play for 1 minute then data will be collected again for 1-3 minutes. Each session will be recorded using the Microsoft Kinect camera. Arm/hand/leg position data will be collected with the Kinect camera, grasp pressure and forces will be collected, toy position and angular data will be collected via Kinect and inertial sensors, and central pressure data will be collected via a pressure mat. General Procedure: A caregiver or parent will be seated at the head of the baby (out of baby's sight) to provide comfort if needed. Infants will be required to be alert and unhampered by clothing with their limbs free to move. They will be placed on their backs and allowed to roll or crawl as long as they stay within the perimeter of the device. If infants become frustrated (cries and is unsettled), the parent will be asked to pick them up and calm them. The trial will be restarted. If several attempts are unsuccessful, the session will be ended and attempted later in the day. We will take precautions to minimize the likelihood of participants experiencing any injury or discomfort. To avoid bumps, bruises or crashing into toys, participants will be supervised at all times by a trained study team member during CHOP sessions, including by a licensed pediatric physical therapist during developmental evaluations, and caregivers will be trained to place infants on their backs during home Gym play sessions. Caregivers will also be able to reposition their infants if he or she is uncomfortable.

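### The plan gives no rule for an infant with fewer than 5 usable days; run as complete-case analyses, its 5-day average and repeated-measures ANOVA would drop that infant

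*Combined protocol and SAP*

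**What the plan says.** For Part B the Design section states: "twenty-four infants will be recruited to participate, including 12 who are developing typically and 12 who are identified as at-risk for neuromotor delay". Each group is split again into a younger and an older stratum, with no cell sizes given. The Procedures section sets measurement on 5 days in a row. Each day has a no-toy run and then a toy run, and the first is used to adjust the second.

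The Analysis Plan calculates an ICC for each metric over the 5 days. If the ICC is about .9, "we will average the 5 days to create a single summary figure for each measurement to test", and the summaries go into t-tests or Wilcoxon tests by age stratum. If it is low, the plan uses a "2-factor ANOVA in repeated measures where day would be the repeated measure and age group and infant type would be the 2 factors". Skewed or zero-heavy metrics go to Poisson or negative binomial regression. The software is SAS; no procedure is named.

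Disruption is foreseen in two places. Under General Procedure, for an infant who cannot be settled: "If several attempts are unsuccessful, the session will be ended and attempted later in the day". Under Subject compensation, should the infant's representative "decide to withdrawal prior to completion of the study, compensation will be prorated". No section states a minimum number of days, how a lost day is treated, whether an infant is replaced, or what loss is expected.

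**The concern.** The ICC, the average and the ANOVA are all described as if every infant has 5 days. Infants of 3 to 11 months must be alert and settled for two runs a day on 5 consecutive days, so some will probably not manage it. Two natural ways of carrying out the plan discard the whole infant when one day is missing: a strict 5-day average, and a classical repeated-measures ANOVA with days laid out as columns (in SAS, the GLM REPEATED statement).

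Two things are at stake. The first is precision, in a sample of about 6 per cell if the age split is even. The second is bias: if the infants who fail sessions tend to be the less able, the completers are a selected group. The ICC that decides which analysis is used would come from the same selected infants. If the handling is settled only after the data are seen, it could also differ from metric to metric.

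**Working it through.** **Plan's own figure.** The 24 is given without alpha, power, effect size, SD or dropout allowance, so it cannot be reproduced. The check is therefore what complete-case handling would do to 24 infants.

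**Inputs from the documents:** 12 v 12 infants, 5 days, two age strata per group, ICC threshold .9. **Assumed:** 6 infants per cell; daily miss rate q, independent across days; two-sided alpha 0.05; 80% power; total single-day variance 1, so effects are in SD units.

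**Step 1. Infants lost under a strict 5-day rule.** P(all 5 days) = (1-q)^5; expected loss = 24 x [1-(1-q)^5].

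| q per day | P(5 days) | Lost of 24 | P(cell of 6 falls to 3 or fewer) |
|---|---|---|---|
| 1% | 0.951 | 1.2 | 0.2% |
| 2% | 0.904 | 2.3 | 1.4% |
| 5% | 0.774 | 5.4 | 13% |
| 10% | 0.590 | 9.8 | 48% |
| 20% | 0.328 | 16.1 | 91% |

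At q = 20% the chance that an infant loses all 5 days is 0.2^5 = 0.03%, so keeping everyone with at least one valid day retains almost all 24 when misses are scattered.

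**Step 2. Precision.** The variance of a k-day mean is ICC + (1-ICC)/k. With full data the SE of a 12 v 12 difference is sqrt(variance x 2/12):
- ICC .5: sqrt(0.60/6) = 0.32
- ICC .9: sqrt(0.92/6) = 0.39

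At q = 10% about 12 x 0.590 = 7.1 infants per group complete:
- ICC .5: sqrt(0.60 x 2/7.1) = 0.41
- ICC .9: sqrt(0.92 x 2/7.1) = 0.51

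Simulation, which lets the number of completers vary, gives 0.41-0.55 for complete cases against 0.32-0.40 using all available days.

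The detectable difference (t-test) is 1.20 SD at 12 v 12 and 1.64 SD at 7 v 7. Within an age stratum it is 1.80 SD at 6 v 6, 2.39 at 4 v 4 and 3.08 at 3 v 3. At 3 v 3 the smallest two-sided exact Wilcoxon p is 2/20 = 0.10, so the planned rank test could not reach 0.05.

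**Step 3. Selection, if it occurs.** Let the log-odds of missing a day fall by 0.5 to 1 per SD of ability (assumed), with ICC .9. The complete-case mean of a group then rises by 0.11-0.18 SD at 5% average daily loss and by 0.21-0.33 SD at 10%. With no dependence on ability the shift is 0. Take a true difference of 1 SD, with 5% loss in typical and 10% in at-risk infants:
- Dependence in both groups: 1 + 0.11 - 0.21 = 0.90 (slope 0.5); 1 + 0.18 - 0.33 = 0.85 (slope 1).
- Dependence in at-risk infants only: 1 - 0.21 = 0.79 (slope 0.5); 1 - 0.33 = 0.67 (slope 1).
- At-risk only, slope 1, with 10% taken as the rate for an at-risk infant of average ability (so the group's average loss is higher): 0.58-0.68 across ICC .9 to .5.

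Available-day means stay at 0.98-1.00 in these settings.

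**Step 4. Cost of keeping incomplete infants.** At ICC .9 a 3-day mean has variance 0.9 + 0.1/3 = 0.933, against 0.9 + 0.1/5 = 0.920 for 5 days. At ICC .5 the figures are 0.667 and 0.600, an 11% increase.

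**The case against.** The plan is silent; it does not exclude anyone. A reader might infer that an incomplete infant cannot be analysed at all, but no section says so. A mean over available days, a variance-component ICC and a mixed-model form of repeated measures would all fit the wording and run in SAS. Other parts of the plan do not depend on 5 days: the daily means and SDs, the correlations with the Bayley instruments, and the count regressions. This stands, and it is why the point is conditional on complete-case handling.

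A reader might also infer that the study will lose many of its 24 infants. The documents give no miss rate, and they take steps against loss: calming and restarting, a retry the same day, daycare testing chosen so that infants can be tested on several days, and testing at home. At 1% per day a strict rule costs about one infant. These steps reduce lost days but do not deal with withdrawal, and they do not say how the remaining incomplete infants are analysed.

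The most tempting inference is that the completers will be the more able at-risk infants. Potential Study Risks does link frustration to motor actions an infant cannot yet perform, and General Procedure ends sessions for unsettled infants. But the frustration risk is not confined to the at-risk group, and nothing ties lost days to ability within it. Infants who attempt less might also be frustrated less, so even the direction is uncertain.

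Finally, averaging whichever days exist is not free of risk. The plan itself anticipates learning. With a day trend, an infant who stops early has an average weighted to early days. That objection stands and shapes the fix.

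**Conclusion.** The concern holds as a conditional one. The plan foresees incomplete infants and describes its main steps for complete data only. If these are run as complete-case analyses, the expected loss ranges from about 1 infant of 24 (1% per day) to about 16 (20% per day), and at 10% random loss the SE rises by roughly a third. Attenuation of a 1 SD difference to roughly 0.6-0.9 SD requires loss that depends on ability, which is plausible but not shown. The lower end further requires that dependence to act in at-risk infants alone. All miss rates, slopes and the even split into cells are assumptions.

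The documents do not support saying that incomplete infants are excluded, that many will be lost, or that the abler at-risk infants will be selected. The change is still worth making, because a better method is available in the named software at almost no cost.

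**What to change.** Amend the Analysis Plan as follows.

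1. High-ICC branch: average all available valid days for each infant. Define a valid day in advance, including whether it needs both the no-toy and the toy run.
2. Low-ICC branch: replace the repeated-measures ANOVA with a linear mixed model (SAS PROC MIXED, REML), with infant type, age group and day as fixed effects and infant as random, using all available days.
3. Estimate the ICC from a mixed model on all available days. If there is a day trend, use the model in item 2 even when the ICC is high.
4. In the Poisson and negative binomial regressions, likewise keep all available days and account for correlation within infant.
5. Report days completed and reasons for loss by group, with a complete-case analysis as sensitivity.

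The cost is wording and standard procedures, with no extra infants, visits or staff. Averages from fewer days are slightly noisier: negligible at ICC .9, larger at low ICC, where the mixed model applies. The change does not recover an infant who withdraws before any valid day, and it does not remove bias if a day is lost because of that day's own performance; item 5 at least makes such loss visible.
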